# 5.3.2 Blinding and Unblinding Procedures

The randomization will be conducted by an organization or individual not involved in day to day the conduct of the study. The investigator will assign the unblinded staff responsible for vaccine preparation, administration, handling and accountability and to ensure that blinding is protected throughout the study procedures and no other site personnel involved in the conduct of the study has access to the information. After assessment of eligibility of a new subject, the Subject Number will be assigned to each subject sequentially in the order they are enrolled. The unblinded staff will prepare and administer vaccine/comparator according to randomization list provided by BIOPHICS. The unblinded staff will be responsible to keep the randomization list in a safe, locked and secured place with no access by other site personnel until the database is locked.

The randomization lists will be provided to GPO for them to label the study vaccine and comparator syringes and then placed in a sealed envelope immediately afterward. It will be opened only after the clinical trial database is declared complete and locked. In the case of any unblinding, researchers must report this in writing to the overseeing ethics committee.

The vial labeling will be done at GPO before study vaccine and comparator are shipped. Study product injected into each participant will be recorded on the Case Report Form (CRF) using the exact allocation code for each product received by each participant.

The allocation codes link treatment identification with each participant identification number. These will be maintained in a secure location, by an individual not involved in the conduct of the study. If the investigator determines that it is necessary to unblind a participant, for example because a participant experiences an SAE possibly related to receipt of study treatment, then the treatment allocation to the participant will be communicated to the investigator.

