# 4. STUDY DESIGN:

# 4.1 Study Design

This is a phase II/III, non-inferiority double-blinded, randomized, and controlled trial to evaluate the safety and immunogenicity of a single dose the GPO seasonal trivalent inactivated influenza vaccine in male and female adults, ages 18 to 49 years old. Participants will be randomized 2:1 to one of two treatment allocations: 630 to vaccine, 315 to comparator. The study will be double blinded, meaning the study participants, investigators, and the sponsor will be unaware of the treatment allocated to each participant until the clinical trial database is declared final and locked.

All participants will be consented for participation and screened for eligibility through medical history review and physical examination. All volunteers will be checked against the inclusion/exclusion criteria. The screening assessments will be performed up to 30 days prior to the first vaccination. The screening procedures for the study including a medical history, vital signs, and physical examination will be performed. A urine pregnancy test will be done in females on screening day, day 0 prior to vaccination. Female volunteers should avoid pregnancy from the screening visit until at least 60 days after the vaccination by using an effective birth control method. The baseline immune response will be performed on day 0 prior to vaccination. One dose of the investigational vaccine or comparator will be given by intramuscular route (preferred injection site will be the deltoid of the non-dominant arm) after blood collection for immunology assays. Total follow-up period is 90 days for immune response and safety.

There will be 4 clinical visits and 1 phone visit as follows:

- Screening Visit (Day -30 to Day 0) Sign informed consent form, screen for eligibility (medical history review and physical examination)
- Day 0 (can be the same day with screening day): Vaccination day, subjects will remain at the clinic for at least 30 minutes for observation of any reactogenicity after vaccination. A diary card will be provided to the subjects for recording such events for 3 days after vaccination (Day 0-3).
- Day 7 (-3, + 7days): Return the diary card and report any adverse events that occur during the first seven days after immunization. Concomitant medication information will be collected.
- Day 21 (+7 days): Blood specimen collection for immune response, follow-up and report VEI any adverse events.

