# 4.5 Comparator

The comparator will be provided in prefilled, single dose, disposable syringes.

Brand Name	A commercially available, licensed vaccine
Common or Non-Proprietary Name of Drug Substance	Influenza vaccine (split virion, inactivated)
Dosage Form(S) and Strength(s)	
 
Suspension, Each 0.5-ml dose contains 15 µg of haemagglutinin (HA) of each of the following three influenza virus strains recommended for southern hemisphere 2017
 
An A/Michigan/45/2015 (H1N1) pdm09-like virus
 
An A/Hong Kong/4801/2014 (H3N2)-like virus
 
A B/Brisbane/60/2008 –like virus
 

Route(s) of Administration	Intramuscular injection
Country from which the clinical supplies were obtained for the Lot to be Used in this Clinical Trial	Thailand
Market status in the above mentioned country	Market Approval

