# 4.6.3 Preparation and Administration

An unblinded staff will prepare and administer vaccine to each participant. None of the unblinded staff will be involved in any reactogenecity and other safety evaluations.

To prepare and administer study product, vaccination facilities and investigators must comply with any applicable regulations. The step-by-step instructions for the investigator (or delegated staff) are as follows:

- Wash hands or use gel disinfectant. Prepare the study vaccine/placebo, needles, syringes, and sharps safety box ahead of time.
- Specific study procedures will be developed and include selecting the appropriate study product. Careful records must be maintained to ensure and document that each participant receives the correct product.
- Make sure sufficient equipment is available to provide every participant with a safe injection and to dispose of injection materials safely.
- Make sure emergency drug and equipment kits are available in both the vaccination area and the observation area.
- Greet the participant in a friendly manner. Ask whether he/she has any questions or concerns about injection and respond to his/her questions and concerns in a truthful and pleasant manner.
- Confirm the participant identity.
- Ensure the participant is seated or lying down.
- Inform the participant that everyone will be preferably vaccinated in the deltoid of their non-dominant arm.
- Put on gloves.
- Instruct the participant to put the hand on the hip and show them the deltoid.
- Disinfect the skin at the injection site.
- Inject intramuscularly the entire contents of the syringe into the deltoid region of the participant's non-dominant arm.
- While the plunger is still depressed, remove the needle from the participant's arm.
- Apply cotton swab with pressure to the injection site.
- Dispose of needle and syringe as one unit in a sharps container that is only used for this MMITTEE study.
   Faculty of tropical medicine
   MAHIDOL UNIVERSITY

APPROVED

- Record the date of vaccination and vaccine vial number on the participant's vaccination record.
- Ask the participant to rest for 30 minutes.
- Blinded staff will provide the diary card, ruler, thermometer and explain how to use them for recording symptoms. Remind them of upcoming phone calls/visits.
- For 30 minutes following vaccination, observe the participant and ask about the participant's well-being.

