#### 14.2 Insurance

GPO, the study sponsor, will have the task of obtaining insurance to cover treatment for study related injuries and other insurance as necessary to meet its ethical or regulatory obligations for conducting this study in Thailand. The insurance contract will be concluded between the "STUDY" and the insurance company prior to the beginning of the trial. The clinical insurance will be covered against legal liability imposed by operation of law to pay damages in respect of injury to any research subject caused by or arising out of participation by the research subject in the clinical trial. If there are any damages under the Clinical Trials Liability Policy, claim can be made to GPO Managing Director, [contact], [name] [contact].

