ClinicalTrials.gov Protocol Registration and Results System (PRS) Receipt Release Date: March 5, 2019

ClinicalTrials.gov ID: NCT03390166

Study Identification

Unique Protocol ID:	Tri Fluvac Vaccine phase 2/3
Brief Title:	Immunogenicity and Safety of Tri Fluvac, a Seasonal Trivalent Inactivated Influenza Vaccine in Healthy Thai Adults
Official Title:	A Phase II/III Double Blinded, Randomized, Controlled, Non-inferiority Trial to Evaluate the Immunogenicity and Safety of Tri Fluvac, a Seasonal Trivalent Inactivated Split Virion Influenza Vaccine, in Healthy Thai Subjects Aged 18-49 Years
Secondary IDs:	

Study Status

Record Verification:	March 2019
Overall Status:	Completed
Study Start:	July 24, 2017 [Actual]
Primary Completion:	March 31, 2018 [Actual]
Study Completion:	February 12, 2019 [Actual

Sponsor/Collaborators

Sponsor:	Mahidol University
Responsible Party:	Principal Investigator Investigator: [name] [[name]] Official Title: [name]: Mahidol University
Collaborators:	The Government Pharmaceutical Organization World Health Organization

Oversight

U.S. FDA-regulated Drug: No

U.S. FDA-regulated Device: No

U.S. FDA IND/IDE: No

Human Subjects Review: Board Status: Approved Approval Number: MUTM 2017-020-01 Board Name: Ethics Comittee of the Faculty of Tropical Medicine Board Affiliation: Faculty of Tropical Medicine, Mahidol University [contact] Email: [contact] Address:

Faculty of Tropical Medicine, Mahidol University [name]

Data Monitoring: Yes

FDA Regulated Intervention: No

Study Description

Brief Summary:	The study is aim to evaluate the immunogenicity and safety with two groups of participants who will received a seasonal trivalent split, inactivated influenza vaccine (A/H1N1; A/H3N2 and B) or an active comparator (licensed influenza vaccine
Detailed Description:	This is a phase II/III, non-inferiority double-blinded, randomized, controlled trial of immunogenicity and safety with two groups of participants who will received a seasonal trivalent split, inactivated influenza vaccine (A/H1N1; A/H3N2 and B) or an active comparator (licensed influenza vaccine).
	A total of about 945 healthy Thai male and female adult volunteers 18 through 49 years of age; 630 participants will be randomized to receive the GPO Tri Fluvac and 315 will receive an active comparator (a 2:1 ratio) (inclusion of ~7% lost to follow-up).

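### Section 4.1 says the sponsor stays blinded until database lock, but section 5.3.2 gives GPO the randomisation lists; the vial-number entry is a possible second route to the allocation

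*Protocol*

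**What the plan says.** Protocol section 4.1 states that "the study participants, investigators, and the sponsor will be unaware of the treatment allocated to each participant" until the database is final and locked. Section 14.2 identifies the sponsor: "GPO, the study sponsor". Section 5.3.2 then says: "The randomization lists will be provided to GPO for them to label the study vaccine and comparator syringes". The same sentence has the lists sealed in an envelope straight after labelling, and the next one keeps the envelope closed until lock.

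Section 5.3.1 says the randomisation blocks of treatment materials go to the study coordination center and nowhere else. The registration record at the front of the SAP names the university as sponsor, lists "The Government Pharmaceutical Organization World Health Organization" as collaborators, and gives masking for participant and investigator only.

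On the injection itself, section 4.6.3 instructs staff: "Record the date of vaccination and vaccine vial number on the participant's vaccination record". Section 4.4.2 describes Tri Fluvac as a two-dose vial. Section 4.5 says: "The comparator will be provided in prefilled, single dose, disposable syringes".

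**The concern.** There are two separate problems. The first is that the sponsor's blinding is stated as fact in one section and contradicted by the labelling procedure in another. GPO makes the test vaccine and takes part in running the trial, so who at GPO has seen the list matters until lock.

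The second is that an identifier which appears to exist for only one arm is to be written on a participant-level record.

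The outcomes most open to influence are the subjective ones. Pain, fatigue and headache are solicited reactions, and solicited events and SAEs are compared between arms at a two-sided 0.05 level (section 11.4). Section 11.4 also relies on a blinded clinician for relatedness, and suspected relatedness feeds the pause rules in section 9.3. Knowledge of the arm could also colour decisions taken before lock on queries and protocol deviations.

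**Working it through.** No arithmetic decides this point. The check is to set the statements side by side.

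**Sponsor blinding**

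- *Who is said to be blinded.* Section 4.1: participants, investigators and sponsor. Registration record: participant and investigator.
- *Who the sponsor is.* Section 14.2: GPO. Section 10.2 agrees, because its reporting to the sponsor is reporting to GPO. Registration record: the university.
- *Who receives randomised material before lock.* Section 5.3.1: only the study coordination center, although it is unclear whether this means the list or the packaged product. Section 5.3.2: GPO receives the lists, and unblinded site staff also hold a list.

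Within the protocol, section 4.1 can be true only if GPO is not the sponsor, which contradicts section 14.2, or if nobody at GPO reads the list, which contradicts section 5.3.2. The envelope is sealed after labelling. It limits how long the list is open; it does not undo the fact that GPO staff have used it.

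The next question is whether those staff are kept apart from the conduct of the trial. GPO appoints the monitors (section 13). It receives SAE reports (section 10.2), and its clinical coordinator forwards them (Appendix B). The sponsor must be satisfied that queries are resolved before lock (section 11.6.3). Deviations are reported to GPO and examined case by case (section 15), without saying by whom or whether that person is blinded. No section says that the labelling staff take no part in these tasks.

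**Vial number**

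For the entry to reveal the arm, two things must both hold.

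1. *The number exists for one arm only.* Sections 4.4.2 and 4.5, read literally, give vials for Tri Fluvac and none for the comparator. The presence or absence of a number would then show the arm, and two participants could share a number. The ceiling is 630 records with a number + 315 without = 945, the whole planned enrolment. However, section 5.3.2 also speaks of vial labelling for study vaccine and comparator together. If that means one code system for both products, the entry reveals nothing. The documents do not settle which is meant.
2. *A person meant to be blinded sees the record.* Section 4.6.3 has unblinded staff prepare and inject, and bars them from safety evaluation. Section 5.3.2 says in general terms that other site personnel have no access to the information. Neither names the vaccination record. Sections 11.6.2 and 13 give monitors direct access to source documents and on-site study documentation, and section 11.6.2 has the monitor act for the sponsor. If the vaccination record is among those documents, a GPO-appointed monitor could read it.

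**What is protected**

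Section 4.1 says that neither the laboratory nor the clinical investigators will know the treatment when HI samples are tested.

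**The case against.** The strongest reply is that the safeguards are real. The list is sealed after labelling. Section 5.3.2 also has the allocation codes kept by someone outside the conduct of the study. At the site, the recording step falls within the work of the unblinded staff, and the text hands over expressly to blinded staff for the diary card. After the 30-minute check, participants record solicited reactions themselves, and investigators need not judge causality for those starting in the solicitation period (section 8.2). SAE causality rests with the investigator and the Safety Medical Team, and data management and analysis with the independent data centre. The protocol also uses vial and syringe loosely, so the vial number may simply be a common label code.

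Much of this stands, and it rules out some stronger conclusions that a reader might draw:

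- *That the blind is broken.* The documents show an inconsistent claim and an unseparated role. They do not show that any assessor learns an allocation.
- *That all 945 records disclose the arm.* That figure is a ceiling under one reading of an ambiguous term, and it also requires blinded readers to have access.
- *That the primary non-inferiority result is compromised through the assay.* The HI titres are read without knowledge of treatment.
- *That GPO's part in the study report is a route before lock.* Section 4.1 ends the blinding at lock, and a report covering all the data comes after it.

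The reply does not remove the conflict between sections 4.1 and 5.3.2, the missing separation within GPO, or the undefined entry on the vaccination record. The registration record does not resolve the conflict either: it adds a disagreement over who the sponsor is and whether the sponsor is masked.

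**Conclusion.** The point holds in a limited form. The sponsor-blinding statement in section 4.1 cannot stand beside sections 5.3.2 and 14.2, and this depends only on the text. The practical risk is smaller than the contradiction suggests, because the list is open at GPO only for labelling. It is not nil, because the labellers are not separated from staff with a role before lock.

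The vial-number entry is a possible route to unblinding. It depends on two assumptions that the documents leave open: that the number belongs to one arm only, and that someone meant to be blinded sees the record.

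No size of bias can be derived. The exposed items are the subjective safety endpoints, relatedness judgements, and decisions on queries and deviations before lock. The change should be made because it is cheap and removes a doubt that could not be resolved after the trial.

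**What to change.** 1. Limit the randomisation list to named GPO labelling staff who have no part, before lock, in monitoring, SAE handling, query resolution or deviation review.
2. Correct section 4.1 to say that these staff are unblinded. Reconcile it with sections 5.3.1 and 5.3.2 on who receives the list and the randomised materials, and with the registration record on who the sponsor is and who is masked.
3. On the participant's vaccination record, enter only the randomisation number or a common arm-neutral code, in the same form for both arms.
4. Keep vial and syringe lot numbers in the accountability log held by the unblinded staff.

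The cost is wording changes and one restricted log. Unblinded site staff already exist under sections 4.6.3 and 5.3.2. Labelling need not move to the data centre, and nothing in the documents shows that the centre could do it. Dose, sample size, endpoints and visits are unchanged.

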# **5.3 Treatment Assignment Procedures**

# 5.3.1 Randomization Procedures

This is a double-blind, randomized, and controlled trial with two groups: vaccine and comparator. Each participant will be assigned a unique screening number assigned by the investigator after signing the informed consent. After an individual is determined to be eligible for study participation, the participant will be randomized by assigning a unique participant identification number from the randomization schedule.

The complete randomization schedule that contains the participant identification number and the corresponding randomization assignment will be produced using computer software prior to the initiation of the study. The permuted randomized block design procedure will be used to generate the randomization schedules using varying block sizes. Treatment assignments will be completely randomized within each block, and the blocks will be ordered (permuted) randomly to ensure treatment balance during enrollment and maintenance of the blind.

The Investigator will maintain a screening/enrollment log. The log will contain essential information including participant ID number, date of screening, gender, date of birth, whether or not the participant meets eligibility criteria, whether the participant is enrolled and date, and if not enrolled, reason why the participant was not enrolled or not randomized.

Once a participant identification number has been assigned, it will not be used again. Additional participants may be randomized into the study in the case of any participant who is randomized but does not receive any study vaccine. Study participants will be randomly assigned to one of the two treatment groups. Blinding through randomization number will be maintained for the investigator who assesses immunogenicity and safety.

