An un-equal randomization of 2:1 (Group V : Group C) lists will be generated by an independent statistician at the Center of Excellence for Biomedical and Public Health Informatics (BIOPHICS) at the Faculty of Tropical Medicine. The computerized randomization will be generated as a block of 3. The sample size of 945 (630 Group V: 315 Group C), the randomization numbers will be generated for 166 blocks. However, with the consideration of any unusual events that might unexpectedly happen during the trial, an extra 4 blocks will be generated as a backup set for VED replacement. This extra list will be kept separately and will be used only when necessary. The randomization will be kept in secured safe-box at BIOPHICS and will be opened only when necessary. The MAHIDOL UNIVERSITY

randomization blocks of treatment materials will be sent only to the study coordination center for study vaccine preparation and distribution to study sites. All other study investigators as well as the volunteers will be blinded from the randomized codes. The codes will be open at the study conclusion or upon special request due to unexpected adverse event occurs. The emergency unblinding process will be done only when there is a special request for ethical and emergency clinical concerns by the sponsor or ethical committee or the principal investigator.

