# 8.7 Relationship to test vaccine (Did the test vaccine cause the adverse experience?):

The determination of the likelihood that the test vaccine caused the adverse experience will be provided by an investigator who is a qualified physician. The investigator's signed/dated initials and date on the source document or worksheet, that supports the causality noted on the AE form, ensures that a medically qualified assessment of causality was done. This initialed document must be retained for the required regulatory time frame. The criteria below are intended as reference guidelines to assist the investigator in assessing the likelihood of a relation the between the test vaccine and the adverse experience based upon the available information.

FACULTY OF TROPICAL MEDICINE MAHIDOL UNIVERSITY An adverse event's relationship to study medication assessment must be made by a medically qualified principal investigator or sub-investigator. The principle investigator or sub-investigator making relationship assessment must document this assessment in the subject's chart or file. The assessment of Causality is reported according to the investigator's best clinical judgment.

- "Related" should be selected if there is evidence of exposure to the test vaccine and the temporal sequence of the AE onset relative to administration of the test vaccine is reasonable. The AE is more likely explained by the test vaccine than by another cause. The AE shows a pattern consistent with previous knowledge of the test vaccine or test vaccine class. Or the AE could have been due to another equally likely cause.
- "Not related" should be selected if the subject did not receive the test vaccine OR temporal sequence of the AE onset relative to administration of the test vaccine is not reasonable OR there is another obvious cause of the AE. OR there is another more likely cause of the AE.
- "Not related" should be selected for subject's with accidental overdose without an associated AE.

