# **10.2 Immediate Reporting of Adverse Experiences to the SPONSOR Serious Adverse Experiences**

Any serious adverse experience, including death due to any cause, which occurs to any subject after immunization throughout the period of the study, whether or not related to the investigational product, must be reported within 24 hours from when the site become aware to the government pharmaceutical organization (GPO) following appendix B: standard operating procedure reporting of serious adverse event, and to the WHO focal point.

All vaccine-related serious and unexpected adverse experiences will be reported on an expedited basis to regulatory agency (ies) but will remain blinded.

The Sponsor is responsible for informing the Data and Safety Monitoring Board (DSMB) of the occurrence of any SAE observed in a trial subject. Detailed description including required information, methods and specific timeframe will be provided in the appendix B: standard operating procedure reporting of serious adverse event.

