# **11.4 Analysis of Safety Endpoints**

The safety profile of the GPO Tri Fluvac will be evaluated by the number and proportion of participants experiencing AEs by severity and relatedness to vaccination of the following five categories for all participants:

- A. Solicited local adverse events, including redness / erythema, swelling / induration, pain within 30 minutes of vaccination and over a 3-day period (Day 0-3) post-vaccination.
- B. Solicited systemic adverse events, including fever, fatigue, malaise, muscle aches, joint aches, chills, nausea, and headache within 30 minutes of vaccination and over a 3-day period (Days 0-3) post-vaccination.
- C. Unsolicited AEs occurring within 90 days post vaccination.
- D. SAEs occurring during the entire study period (Days 0-90).

Occurrences of all events will be reported and summarized according to event severity, as "any local AE", or "any systemic AE", and by relationship to administration of study product, as deemed by a blinded study clinician. Percentage of participants experiencing each reaction or event, or at least one reaction or event will be calculated along with two-sided exact 95% CIs. No statistical testing will be performed for unsolicited AEs; including SAEs. The percentage of participants with solicited AE and SAEs will be compared between vaccine and comparator groups and a two-sided p-value of 0.05 will be considered statistically significant.

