# 6.3 Reviewing of SAE report and writing draft notification of Suspected Unexpected Serious Adverse Reaction (SUSAR) by SMT

- 6.3.1 Evaluation of causality relationship and expectedness by SMT.
- 6.3.2 If need clarification, SMT can directly communicate with PI with copy of the communication to GPO Clinical Coordinator.

Electronic File Name & Path:	Reviewed By (CRCG) : Man
Q:\CC\_Section\SOPs\SOP-CC\SOP CC-001\SOP CC-001-01\ SOP No.	F 1 300
CC-001-01	Date: 23 Feb 17

Standard Operating Procedure

			-	Restricted circulation
Group	:	Clinical Research Co-ordination Group	SOP No.	: CC-001-01
Title	:	REPORTING OF SERIOUS ADVERSE	Page No	:6 of 8
		EVENT (SAE)		

- 6.3.3 SMT writes causality assessment and decision on qualification for SUSAR in topic 35-37 of Attachment No. 01 (SAE Report Form for Clinical Trial) and sends signed Attachment No. 01 to GPO Clinical Coordinator within 72 hours by scanned e-mail. If SUSAR is justified, Attachment No. 02 (Thai FDA Format) is needed to fill by SMT.
- 6.3.4 GPO Clinical Coordinator submits signed Attachment No. 01 to PI within 24 hours and submits Attachment No. 02 to Thai FDA within 24 hours (if required).
- 6.3.5 All communications are archived in the Investigator Site File (ISF) and the Sponsor file.
- 6.4 It is noted that timing for SAE report stated in this SOP (6.1-6.3) are expressed for SAE with fatal or life-threatening outcomes. For other SAEs, timing can be extended to be double of the time for SAE with fatal or life-threatening outcomes.
- 6.5 Qualification for SUSAR and writing final report of SUSAR by SMT.
- 6.5.1 SMT must make a decision on qualification for SUSAR. If SUSAR is confirmed, SMT writes a final report of SUSAR and sends the signed report by scanned e-mail to GPO Clinical Coordinator within 5 days.
- 6.5.2 GPO Clinical Coordinator submits the final report of SUSAR within 3 days to Thai FDA, Investigator and DSMB and copies to clinical monitor.
- 6.5.3 For serious and unexpected ADR, SMT must decide if there is a need to unblind the case. Unblinding can be done as described in SOP: Emergency Unblinding of Randomization Code (SOP No. CC-002-XX).
- 6.5.4 The final report of SUSAR and the emergency unblinding form filled by SMT (if available) must be kept in the Sponsor file.
- 6.6 Update of ICF by PI within 1 month.
- 6.7 Update of Investigator's Brochure by GPO within 1 month.

-	Electronic File Name & Path:	Review	ved By (C	RCG): Ins of

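### The protocol's code-break rules disagree on who decides, on what trigger and who is told, and nothing keeps the causality rating used in the safety analysis blinded after a break

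*Protocol*

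**What the plan says.** Section 4.1 keeps participants, investigators and sponsor unaware of allocation until the database is locked and states no exception there. Section 5.3.1 adds: "Blinding through randomization number will be maintained for the investigator who assesses immunogenicity and safety". Its last paragraph then allows codes to be opened on special request after an unexpected adverse event. The same paragraph confines the emergency process to special requests on ethical and emergency clinical grounds from the sponsor, the ethics committee or the principal investigator.

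Section 5.3.2 describes another route: "If the investigator determines that it is necessary to unblind a participant, for example because a participant experiences an SAE possibly related" to study treatment, "then the treatment allocation to the participant will be communicated to the investigator".

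Appendix B (the SAE reporting SOP), item 6.5.3, names a different decision-maker: "For serious and unexpected ADR, SMT must decide if there is a need to unblind the case". It refers to a separate emergency-unblinding SOP (CC-002) for the procedure.

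On causality, section 8.7 says the determination "will be provided by an investigator who is a qualified physician". It directs a Not related rating when, among other reasons, the participant did not receive the test vaccine. Section 11.4 summarises events "by relationship to administration of study product, as deemed by a blinded study clinician", and the SAP synopsis repeats this under the primary safety endpoints.

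**The concern.** A reader of these sections cannot tell who may open a code, on what grounds, or who then learns the allocation. That alone calls for reconciliation.

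It also affects the data. The investigator who receives the code under 5.3.2 may be the investigator who rates causality under 8.7. No available text requires the rating to be fixed before the break, or passes it to someone who stays blinded. Relatedness of AEs and SAEs is tabulated by arm in SAP TREF 2.1 and 2.4, and one SAE suspected to be vaccine related triggers the first stopping rule in section 9.3. If the rating is settled with the allocation known, the tables no longer show what 11.4 says they show.

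**Working it through.** The plan gives no figure to reproduce. The check compares the passages and adds one short illustration.

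**Step 1: the rules side by side.**

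| Place | Who decides | Trigger | Who learns the code |
|---|---|---|---|
| 4.1 | not stated | none before database lock | no participant, investigator or sponsor |
| 5.3.1, on the assessor | not stated | none | safety-assessing investigator stays blinded |
| 5.3.1, on opening codes | special request, requester not named | unexpected adverse event | not stated |
| 5.3.1, on emergencies | request by sponsor, ethics committee or principal investigator | only ethical and emergency clinical concerns | not stated |
| 5.3.2 | the investigator | own finding of necessity; example is a possibly related SAE | the investigator |
| Appendix B, 6.5.3 | Safety Medical Team | serious and unexpected reaction | left to the CC-002 SOP |

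Decision-maker and trigger differ between rows. Only 5.3.2 says that the allocation goes to the investigator.

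**Step 2: order of rating and code break.** Appendix B has the Safety Medical Team assess causality (6.3.1 and 6.3.3) before it decides on unblinding (6.5.3). The 5.3.2 route is not tied to that order. The documents also do not say whether the investigator's or the team's rating is the one that 11.4 summarises.

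**Step 3: why a known code changes the rating.** Read test vaccine in 8.7 as Tri Fluvac. Once a participant is known to have had the comparator, the 8.7 criterion by itself gives Not related. The same event rated blind could be Related. Applying the protocol as written after a break therefore removes related events from one arm only, without any subjective bias.

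**Step 4: size, as an illustration.** Inputs: allocation 630 to 315 of 945 (Protocol 11.2). Assumptions: no true difference between arms, independent events, every possibly related SAE unblinded, and the 8.7 criterion applied afterwards.

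- Comparator share of such SAEs: 315/945 = 1/3.
- Chance that at least one of k is reclassified: 1 − (2/3)^k.
- k = 1: 1 − 0.667 = 33%. k = 2: 1 − 0.444 = 56%. k = 3: 1 − 0.296 = 70%.
- With three events split 2 to 1 as expected, blinded rates are 2/630 = 0.32% and 1/315 = 0.32%. After reclassification they are 0.32% and 0%.

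Under these assumptions the distortion makes Tri Fluvac look worse than the comparator. For Tri Fluvac recipients, knowing the code could move the rating either way.

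**The case against.** Much can be said for the plan, and several stronger readings fail.

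- **Automatic disclosure.** A reader might infer that every possibly related SAE is unblinded. Section 5.3.2 does not say so: the investigator must first find unblinding necessary, and the SAE is only an example.
- **A ban in 5.3.1.** Section 5.3.1 has its own adverse-event exception, and the principal investigator may request an emergency break. The dispute is over trigger and decision-maker, not over whether any investigator may ever learn a code.
- **Section 10.2.** Its statement that vaccine-related serious unexpected events "will be reported on an expedited basis to regulatory agency (ies) but will remain blinded" concerns reports to regulators. It does not say whether an investigator may see the code, so it does not contradict 5.3.2.
- **Unblinded before any rating.** Calling an SAE possibly related implies that a first judgement exists, and 8.7 requires signed and dated causality documentation. The supportable risk is a rating finalised or revised after the break.
- **Leak through the blocks.** Section 5.3.1 says "The computerized randomization will be generated as a block of 3". If that governs and block membership can be inferred, one disclosed comparator recipient reveals two Tri Fluvac recipients. But 5.3.1 also specifies varying block sizes, so this cannot be asserted.
- **Existing controls.** Any unblinding must be reported in writing to the ethics committee (5.3.2), and a completed unblinding form is filed (Appendix B, 6.5.4). The CC-002 SOP, not available here, may settle the order of rating and break.

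These points narrow the concern. They do not remove it: the controls record a break but do not protect the rating, and the protocol sections still disagree.

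**Conclusion.** The point holds in limited form. Sections 4.1, 5.3.1, 5.3.2 and Appendix B 6.5.3 conflict on who may break the code, on what trigger and who is told. A causality rating settled after a break is not the blinded rating that 11.4 and the SAP describe, and under 8.7 it would selectively remove comparator-arm related events.

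The number of possibly related SAEs is not given, and the 33% to 70% range rests on the assumptions in step 4, which are deliberately extreme. The phase I/II figure of two related AEs among 200 vaccinated concerns AEs, not SAEs, and does not help. The argument also assumes that test vaccine in 8.7 means Tri Fluvac, and that an 8.7 rating of Not related falls in the unrelated row of TREF 2.1. The SAP footnote uses a graded scale that 8.7 does not define.

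A reader might infer that each such event decides the safety conclusion. The documents do not support that: TREF 2.1 and 2.4 are descriptive, and 11.4 compares percentages with SAEs, not with related SAEs. The immunogenicity non-inferiority criteria do not use these ratings. The change should be made because it is nearly free and protects part of the primary safety summary.

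**What to change.** 1. Reconcile 4.1, 5.3.1, 5.3.2, Appendix B 6.5.3 and the CC-002 SOP into one rule on who may request or decide a code break, on what trigger, and who is told. Emergency access need not be narrowed.
2. Require seriousness, severity and causality to be recorded, signed and dated before any code is opened, or have them rated by a clinician who stays blinded. Keep any later revision as a separate entry.
3. State in 11.4 and the SAP that only this blinded rating enters TREF 2.1 and 2.4, and align the SAP's relatedness categories with 8.7.
4. Add a SAP listing of code breaks by arm, with the dates of break and rating. None of the existing listings (Appendices 01 to 11) covers them.
5. Reconcile 8.7 and the stopping rules in 9.3 on which causality rating the first rule refers to.

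The cost is protocol, SOP and SAP wording and one listing. The SAE process already captures causality, so no new assessment is needed if the existing rating is signed first.
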